6.2.2 Visit 2 (Post-op)

As part of routine post-op monitoring, participants will stay overnight in the hospital for monitoring. They may be discharged the following day or up to 3 days later depending upon their clinical status. Prior to discharge, we will conduct Visit 2 assessment.

The following procedures will be collected at Visit 2:

- Interim medical history review
- Physical Exam
- Vital Signs
- Routine Clinical Labs/Phlebotomy: such as a complete blood count (CBC) and chemistry profiles
- Research EGD (Esophagogastroduodenoscopy)
- Adverse Event/Unanticipated Problem assessment and recording

The Research EGD may be conducted immediately following the ablation or up to 2 days post ablation procedure.

6.2.3 Visit 3 (Post ablation Month 1)

Participants will be scheduled for a routine follow up visit post-ablation by the clinical staff at approximately 1 month after having had the ablation procedure.

The following procedures will be collected at Visit 3:

- Interim medical history review /concomitant medications
- Physical Exam & Vital Signs
- Adverse Event/Unanticipated Problem assessment and recording

Participants that do not return for their clinical follow up will be contacted by the research staff at approximately 1 month to collect interim history, medication use, and adverse event information.

6.2.4 Follow up data collection (Post ablation Month 3,6,12)

Participants will be scheduled for routine follow up visits post-ablation by the clinical staff at approximately 3 months, 6 months, and 12 months after having had the ablation procedure.

The following data will be collected from the EMR if available:

- Interim medical history/concomitant medications
- Physical Exam & Vital Signs

6.3 Rescue Therapy

The EnsoETM device will be removed and replaced if at any time there is evidence of a potential device malfunction, such as the inability to adequately reach target cooling temperature. The device can be easily removed and replaced during the ablation procedure if needed. Should evidence of continued malfunction occur after replacement of the study device, the EnsoETM will be removed and replaced with the standard temperature probe allowing the patient to undergo the standard ablation procedure.

6.4 Unscheduled Visits

The research team will assess for the occurrence of any adverse event(s) / unanticipated problem (s) should a patient present for any unscheduled visit to University of Pennsylvania Cardiology or GI clinical practice up through 30 days following the ablation procedure.

6.5 Subject Withdrawal

Subjects may withdraw from the study at any time without impact to their care. They may also be discontinued from the study at the discretion of the Investigator for lack of adherence to study procedures or visit schedules, AEs, or should it become clinically necessary to deviate from the study protocol during the course of the ablation procedure. The Investigator may also withdraw subjects who violate the study plan, or to protect the subject for reasons of safety or for administrative reasons. It will be documented whether or not each subject completes the clinical study. We will attempt to have one final visit or contact at approximately 30 days to follow up regarding adverse events for participants who withdraw prior to the 30 day follow up visit.

6.5.1 Data Collection and Follow-up for Withdrawn Subjects

We will attempt to have one final visit or contact at approximately 30 days to follow up regarding adverse events for participants who withdraw prior to the 30 day follow up visit. During this contact they will be asked for permission to have the study team look into their survival status via their electronic medical records and publicly available means.

7 Statistical Plan

Primary Endpoint

The primary endpoint of this study will be the occurrence rate of esophageal thermal injury, the severity (Grade 1-4) of thermal injuries, and number of distinct injuries present. This will be assessed by blinded gastroenterologist using images captured during the EGD procedure.

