5.2 Intervention Regimen

Patients who are randomized to the EnsoETM device will have the device placed in the electrophysiology laboratory following intubation and prior to the ablation procedure. The device will remain in place until the ablation procedure is completed. These patients will undergo posterior wall ablation when the EnsoETM device has reached a temperature of 4-6°C for at least 2 minutes. The device will be set to nominal temperature (no cooling) during other aspects of the procedure.

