5.5 Blinding

Due to the nature of this study, the physicians will not be blinded to the randomization assignment, however participants will be blinded. Once a subject is randomized, the research team will receive the randomization assignment (EnsoETM or SOC) and proceed with the procedures per the assignment. In addition, the gastroenterologist interpreting the EGD study for the primary endpoint assessment will be blinded to the participants' randomization.

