8.6 Unblinding Procedures

The study team will not be blinded to the randomization assignment. The study team will be instructed to maintain blinding for participants until after their EGD unless a participant has a clinical need to know their randomization assignment. The decision to unblind will be at the discretion of the study PIs and only if unblinding would change clinical care. Unblinding for safety reasons will be recorded in study records and it will be reported to the IRB and the funding sponsor at the time of continuing review. Though we have found it hard to ensure participants stay blinded while in the hospital, we have instructed the extended care team to limit disclosure to the patient until after the EGD at the earliest. The EGD images will be de-identified and batch reviewed to ensure reviewers are not aware of the treatment arm, and all other endpoints are objective/quantitative and thus would not change based on blinding.

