8.7 Data and Safety Monitoring

It is the responsibility of the Principal Investigator to oversee the safety of the study. The Principal Investigator and designated members of the study team will be responsible for monitoring subject safety and applicable reporting to the IRB and study sponsor. This safety monitoring will include careful assessment of eligibility and detailed assessment and appropriate reporting of adverse events as noted above. Grading of EGDs will be done by a single physician contracted to perform the reads. Data collected on the study will be reviewed after 10 people are enrolled in the study. Another data review will occur at 20 and 40 patients enrolled.

9 Study Administration, Data Handling and Record Keeping

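### Blinding covers the reader of the EGD images but not whoever records them, and no capture standard is set, so the primary endpoint is open to arm-dependent lesion capture

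*Combined protocol and SAP*

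**What the plan says.** All references are to the combined protocol and SAP.

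- **What is graded.** Section 7 (Primary Endpoint) names occurrence, severity grade and number of distinct injuries, and adds: "This will be assessed by blinded gastroenterologist using images captured during the EGD procedure". No section describes a live research read or video.
- **Who grades.** Section 8.7: "Grading of EGDs will be done by a single physician contracted to perform the reads". Section 8.6 has the images stripped of identifiers and read in batches.
- **Who is blinded.** Section 5.5: "Due to the nature of this study, the physicians will not be blinded to the randomization assignment, however participants will be blinded". It then adds one more blinded role: "the gastroenterologist interpreting the EGD study for the primary endpoint assessment will be blinded to the participants' randomization". The person performing the EGD is not mentioned.
- **When the EGD happens.** Section 6.2.2: "The Research EGD may be conducted immediately following the ablation", or up to 2 days later. Section 5.2 says of the cooling device: "The device will remain in place until the ablation procedure is completed".
- **Ward blinding.** Section 8.6 concedes that "we have found it hard to ensure participants stay blinded while in the hospital" and records an instruction to the care team to limit what the patient is told until after the EGD.
- **Clinical report.** Section 3.1.2 provides a separate clinical interpretation of the EGD in the medical record, with no statement that it is blinded. The same section limits ablation-related injury to the anterior wall, 20 to 30 cm from the incisors, and defines the four grades.

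**The concern.** An endoscopic endpoint is produced in two steps: someone examines the esophagus and records images, then someone grades them. The plan protects the second step well and says nothing about the first. If the person recording knows the arm, the time spent looking, the areas covered and the number of images stored can differ between arms without any intent to bias. De-identified batch reading does not help, because a lesion absent from the images counts as no lesion.

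All three primary components depend on what was recorded, and so does the lesion score in Section 7.3, which is built from counts of distinct lesions by grade. Section 7.2 intends the results to inform larger studies. With 30 patients per arm, a few missed patients would matter to the estimate carried forward.

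**Working it through.** **Step 1: which stage each safeguard covers.**

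| Provision | Recording images | Grading images |
|---|---|---|
| Blinded interpreting gastroenterologist (5.5, 7) | not covered | covered |
| De-identified batch review (8.6) | not covered | covered |
| Single contracted reader (8.7) | not covered | covered |
| Attribution zone and grades (3.1.2) | defines what counts; does not require the zone to be fully imaged | covered |
| Limit on disclosure to patients (8.6) | aimed at the patient, not the endoscopist | not relevant |

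No provision covers recording. The documents do not say who performs the research EGD, where it takes place, who selects frames, or whether all images go to the reader. Sections 5.2 and 6.2.2 together make it possible, but do not state, that the endoscopist sees or learns the arm.

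**Step 2: size, as an illustration.** The plan gives no figure to reproduce; Section 7.2 says a power calculation could not be done accurately.

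Inputs from the documents: control injury rate r = 0.35 (Section 7.2) and n = 30 per arm (Section 3.1). Assumptions: the same true rate in both arms, complete capture in the control arm, capture of a fraction s of injured patients in the device arm, and a two-sided Fisher test at 0.05. The plan states no test or alpha.

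- Observed device-arm rate = r × s
- Spurious difference = r × (1 − s)
- Expected patients missed = 30 × r × (1 − s)
- Apparent odds ratio = [rs/(1 − rs)] / [r/(1 − r)]
- False-positive rate = summed binomial probability of all pairs of counts (0 to 30 in each arm) with Fisher p < 0.05

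| s | Observed rate | Spurious difference | Patients missed | Apparent odds ratio | False-positive rate |
|---|---|---|---|---|---|
| 1.0 | 35.0% | 0 points | 0 | 1.00 | 2.6% |
| 0.9 | 31.5% | 3.5 points | 1.05 | 0.85 | 3.2% |
| 0.8 | 28.0% | 7.0 points | 2.10 | 0.72 | 5.2% |
| 0.7 | 24.5% | 10.5 points | 3.15 | 0.60 | 9.1% |

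Example at s = 0.7: 0.35 × 0.30 = 0.105, and 30 × 0.105 = 3.15 patients. The odds ratio is (0.245/0.755)/(0.35/0.65) = 0.60.

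If the loss falls in the control arm instead, the difference changes sign and cooling looks worse than it is.

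**Step 3: the weighted score.** Section 7.3 weights Grades 1 to 4 by 1, 10, 100 and 1000. Take a hypothetical arm of ten injured patients with one lesion each: six Grade 1, three Grade 2, one Grade 3. The total is 6 + 30 + 100 = 136. Missing three Grade 1 patients (30% of the injured) removes 3/136, about 2%. Missing the one Grade 3 patient (10% of the injured) removes 100/136, about 74%. The score effect therefore cannot be read from the proportion of patients missed.

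**The case against.** The strongest reply is that the plan already blinds the step where judgment is most visible, with one contracted reader, de-identified batches, a fixed attribution zone and defined grades. A competent endoscopist would be expected to document what is seen, and the clinical report gives a second record in which a lesion seen but not captured might appear. This is a small pilot without a power calculation, and the miss rates above have no basis in the documents.

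Much of this stands. The grading safeguards are sound and the clinical report is a useful cross-check. But that report is not the endpoint and is not stated to be blinded, and nothing fixes how faint or multiple lesions are recorded for research.

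Four stronger readings are tempting and are not supported:

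- **That the endoscopist picks the images with the device in view.** The documents give neither the EGD location nor who selects frames. Section 6.2.2 lists the EGD as a post-operative assessment before discharge.
- **That Section 8.6 admits the arm leaks to the endoscopist.** The admission concerns participants only.
- **That the lesion score must shift at least in proportion to the patients missed.** Step 3 shows that it need not.
- **That the result is biased, or biased toward the device.** The documents show an unprotected step, not a bias. A more careful search in the cooled arm would push the other way.

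**Conclusion.** The concern holds as an unprotected step in how the primary endpoint is obtained. Blinding stops at interpretation, the plan does not keep the person performing the EGD unaware of the arm, and capture is not standardised. Arm-dependent capture is therefore possible for occurrence, grade and number of injuries, and blinded reading cannot correct it.

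The size is unknown. Under the assumed one-arm miss rates of 10% to 30%, the spurious difference is 3.5 to 10.5 points, about 1 to 3 of 30 patients. The effect on the score could be much smaller or larger. This rests on the plan's 35% rate applied to both arms, complete capture in the other arm, and miss rates chosen for illustration. That the endoscopist may know the arm is an inference from the timing provisions and the wording of Section 5.5. The change is worth making because it is cheap and acts on all three primary components.

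**What to change.** Amend Sections 5.5 and 6.2.2 to require that:

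1. the person performing the research EGD is not told the arm, and the device, temperature probe and cooling console are out of view before the EGD where feasible;
2. capture is the same for every patient: either continuous video or a fixed set of stills covering 20 to 30 cm from the incisors;
3. the full recording goes unselected to the existing blinded reader;
4. a short form records whether the endoscopist knew the arm.

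The clinical report can be compared with the research read as a descriptive cross-check, without replacing it.

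The cost is a few minutes of recording and larger files. No extra reader, procedure or patient is needed. The past tense in Section 8.6 suggests that enrolment may have begun. If so, the rule can apply only to later EGDs, and capture would differ between early and late patients; the date of change should be recorded and the two groups described separately.

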7.1 Secondary Endpoints

Secondary endpoints include:

1. Evaluation of posterior wall ablation parameters:
 - Number of posterior wall ablations
 - Total posterior wall ablation time
 - Biophysical parameters (power, time, temperature, impedance changes, contact force)
2. Occurrence and location of any acute PV reconnection
3. Freedom from AF at 3 months, 6 months, and 12 months

7.2 Sample Size and Power Determination

Based on prior studies, esophageal injury following ablation is anticipated to be approximately 35% in the control group. However, as we do not know the occurrence rate of the primary outcome of esophageal injury using the Penn ablation technique that would represent the control group nor in the device arm we are unable to accurately perform a power calculation for this pilot study. We believe that a total of 30 patients for each group will be required to yield the necessary pilot data to make an appropriate conclusion regarding the potential utility of esophageal thermal cooling using this device on the reduction of esophageal thermal injury. It is also anticipated that data from this pilot study can be used for planning future larger studies.

7.3 Statistical Methods

We will utilize a calculated esophageal lesion score to account for both lesion severity and the number of distinct lesions identified per patient for comparison between patient groups. The score will be a four-digit number WXYZ where each digit represents the number of lesions at each severity level per patient defined as: Z: Grade 1; Y: Grade 2; X: Grade 3; W: Grade 4. This will be inputted into the following formula in order to calculate the thermal injury score for each patient: $Score = 1000*W + 100*X + 10*Y + Z$.

7.3.1 Baseline Data

Baseline and demographic characteristics will be summarized by standard descriptive statistics (including mean and standard deviation for continuous variables such as age and standard percentages for categorical variables such as gender).

7.3.2 Efficacy Analysis

This is a pilot study to determine the potential role of the EnsoETM device for the prevention and/or reduction of esophageal thermal injury during atrial fibrillation ablation procedures. This analysis will be performed using the calculated esophageal lesions score as described above based on the primary outcome data of thermal injury occurrence rate, severity (Grade 1-4) of injuries, and number of distinct injuries present between study groups.

7.3.3 Interim Safety Analysis

All subjects entered into the study and randomized at the baseline visit will have detailed information collected on adverse events for the overall study safety analysis. An interim safety analysis will be performed after the first 10

subjects are enrolled in the trial. At this time the safety and tolerability of the study device and research EGD procedure will be assessed and if, deemed safe and appropriate, enrollment will continue up to 70 subjects.

7.4 Subject Population(s) for Analysis

All patients enrolled, randomized to a study arm, and complete the initial phase of the study (ablation procedure and EGD) will be included for analysis.

8 Safety and Adverse Events

8.1 Definitions

8.1.1 Unanticipated Adverse Device Effect

An Unanticipated Device Effect is any serious adverse effect on health or safety, or any life-threatening problem or death caused by, or associated with a device, if that effect, problem, or death was not previously identified in nature, severity, or degree of incidence in the investigational plan or application (including a supplementary plan or application), or any other unanticipated serious problem associated with a device that relates to the rights, safety, or welfare of subjects.

Serious injury:

Any injury or illness that is any one of the following:

- life-threatening
- results in permanent impairment of a body function or permanent damage to body structure
- necessitates medical or surgical intervention to preclude permanent impairment of a body function or permanent damage to a body structure

8.1.2 Adverse Event

An **adverse event** (AE) is any symptom, sign, illness or experience that develops or worsens in severity during the course of the study. Intercurrent illnesses or injuries should be regarded as adverse events. Abnormal results of diagnostic procedures are considered to be adverse events if the abnormality:

- results in study withdrawal
- is associated with a serious adverse event
- is associated with clinical signs or symptoms
- leads to additional treatment or to further diagnostic tests
- is considered by the investigator to be of clinical significance

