1.2 Background and Relevant Literature

Due to the low occurrence rate of AEF, prior studies aimed to develop strategies to prevent it have used the occurrence of esophageal injury as assessed with endoscopy as a surrogate endpoint. The occurrence rate of esophageal injury has varied depending on the reporting center, timing of endoscopy, and the ablation technique utilized. Esophageal ulceration is likely the initial injury that leads to AEF formation and is probably present within hours to days of the ablation procedure. Deneke et al. have assessed the outcomes of >800 patients who underwent first-time catheter ablation of AF followed by EGD within 4 days of the procedure. They found that 82% of patients had EGD without esophageal lesions and no subsequent esophageal events. Of the patients with esophageal abnormalities, two-thirds had erythema with no further complications. The 5 documented esophageal perforations occurred in patients with esophageal ulceration (ratio of esophageal perforation to ulcer, 1:10)². In a study performed by one of the study investigators at a previous institution that utilizes a similar technique as Penn, [name], et al. found evidence of esophageal thermal injury in 9/20 (45%) on EGD the day after the ablation procedure³.

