3.1.4 Follow Up Data Collection Phase

The standard of care follow up visits that typically occur following an atrial fibrillation ablation procedure will be documented by the clinical care team in the participant's electronic medical record (EMR) and will be reviewed by research staff for follow up data collection. This will occur at approximately 3 months, 6 months and 12 months. The research team will collect the following data if available:

- Physical Exam

- Interim History and concomitant medication use
- Vital signs
- Atrial fibrillation recurrence

If a participant does not attend their clinical follow up visits, the research staff will attempt to contact the participant by phone to review their interim history, medication use and collect atrial fibrillation recurrence information.

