8.2 Recording of Adverse Events

At each contact with the subject, the investigator will seek information on adverse events by specific questioning and, as appropriate, by examination. Information on all adverse events will be recorded immediately in the source document, and also in the appropriate adverse event case report form (CRF). All clearly related signs, symptoms, and clinically significant abnormal diagnostic procedures results should be recorded in the source document, though should be grouped under one diagnosis.

All adverse events occurring during the study period (consent through Visit 3 – 1 month follow up) will be recorded. The clinical course of each event will be followed until resolution, stabilization, or until it has been determined that the study intervention or participation is not the cause. Serious adverse events that are still ongoing at the end of the study period will be followed up to determine the final outcome. Any serious adverse event that occurs after the study period and is considered to be possibly related to the study intervention or study participation will be recorded and reported immediately.

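### Section 8.1.2 leaves open whether an asymptomatic ulcer on the Day 0-2 EGD is an adverse event, and late esophageal complications can be captured unequally between arms

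*Combined protocol and SAP*

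**What the plan says.** **Is the lesion an AE?** Section 8.1.2 first treats illnesses and injuries arising during the study as AEs. The next sentence gives a narrower rule for tests: "Abnormal results of diagnostic procedures are considered to be adverse events if the abnormality" leads to withdrawal, goes with a serious event, goes with signs or symptoms, prompts treatment or more tests, or is clinically significant in the investigator's view. Section 3.1.2 grades superficial and deep ulceration (Grades 2 and 3) as moderate and significant injury. Section 3.2.3 mentions the EGD under the safety endpoints. No section says how a graded lesion enters AE recording. Sections 5.5 and 8.6 state that the physicians and study team know the assignment.

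**What follows from AE status?** Under 8.2, "The clinical course of each event will be followed until resolution, stabilization, or until it has been determined" that the study is not the cause. This applies to recorded AEs.

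**How long are events sought?** Sections 8.2 and 8.4 run the AE period from consent to Visit 3, which 3.1.3 sets at Day 30, minus 14 or plus 30 days. Section 6.4 adds AE assessment at "any unscheduled visit to University of Pennsylvania Cardiology or GI clinical practice up through 30 days" after ablation. At 3, 6 and 12 months, 3.1.4 and 6.2.4 take interim history, medication, examination and vital signs from the chart, and 3.1.4 adds AF recurrence. If a visit is missed, staff try to telephone to "review their interim history, medication use and collect atrial fibrillation recurrence information". After the AE period, 8.2 requires recording of a serious event only if it is considered possibly related to the study intervention or to taking part.

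**Why ulcers matter.** Section 1.2 reports from a registry that "The 5 documented esophageal perforations occurred in patients with esophageal ulceration", with a "ratio of esophageal perforation to ulcer, 1:10".

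**The concern.** The protocol's background identifies patients with ulceration as the ones in whom perforation occurred, yet the safety section has no rule written for them. Whether a symptomless ulcer becomes a documented event can depend on which of two adjacent sentences is applied and, under the second, on the opinion of someone who knows the arm.

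The later safety net depends on judged relatedness, and relatedness does not mean the same thing in the two arms. A device patient had the study device in the esophagus. A control patient had a standard ablation with a standard probe, and only the EGD was research. At stake is whether a rare but serious esophageal outcome is ascertained completely and by the same rule in both arms.

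**Working it through.** **1. Reproduce the protocol's ratio.** Inputs from 1.2: more than 800 patients, 82% without lesions, two-thirds of lesions erythema, 5 perforations. I take N = 800 as the lower bound and assume that every lesion other than erythema is an ulcer.

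- Lesions: 800 × (1 − 0.82) = 144
- Erythema: 144 × 2/3 = 96
- Ulcers: 144 − 96 = 48
- Perforations per ulcer: 5/48 = 10.4%, or 1 in 9.6

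For an assumed N of 800 to 899 the ratio runs from 1:9.6 to 1:10.8, so the stated 1:10 is reproduced. The exact (Clopper-Pearson) 95% interval is 3.5% to 22.7% for 5/48, and 3.3% to 21.8% for 5/50.

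**2. Test whether it can be carried over.** The registry's rate over all patients, applied to 60, gives 60 × 5/800 = 0.375 events. The AEF incidence in 1.1 (0.02% to 0.11%) gives 60 × 0.0002 = 0.012 to 60 × 0.0011 = 0.066. The two background sources differ by a factor of 0.375/0.066 = 5.7 to 0.375/0.012 = 31. Perforation and fistula are not the same outcome, but a gap of this size rules out a forecast. The registry shows where the risk lies, not how large it is here.

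**3. Walk one case through 8.1.2.** Take a Grade 2 ulcer with no symptoms, no treatment, no further test, no withdrawal and no serious event. Under the injury sentence it is an AE. Under the diagnostic-results sentence four of the five conditions fail, and the fifth is the investigator's opinion. The text supports both answers.

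**4. Set out the time windows.**

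- Visit 3 falls between Day 30 − 14 = Day 16 and Day 30 + 30 = Day 60. It is the next planned contact whether the EGD was normal or showed an ulcer not recorded as an AE.
- Section 6.4 names two Penn services and stops at Day 30. If Visit 3 is on Day 16, the AE period in 8.2 and 8.4 closes 14 days before 6.4 does. If it is on Day 60, 6.4 stops 30 days before Visit 3.
- Months 3, 6 and 12 have general history but no AE or esophageal field.

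**5. Compare a late perforation across arms under 8.2.** In the device arm, a possible relation to the study device is easily entertained, so the event is recorded. In a control it can be attributed to standard ablation, which 8.2 does not require to be recorded. The same clinical event can give two different study records.

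**The case against.** Much of the opposing case stands.

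- **An ulcer may already be an AE.** On the injury sentence it is one, and 8.2 follows it. A reader might infer that the plan excludes ulcers from AE status or leaves them unfollowed. The documents do not say that. They are ambiguous, and any one of the five conditions also suffices.
- **Later events are not ignored.** A reader might infer that nothing planned would find a late complication. That is too strong. Interim history at 3, 6 and 12 months can reveal one, 8.2 has AEs sought by specific questioning at contacts, and 8.1.7 has subjects told at the last scheduled visit to report later events they think may be study-related. What is missing is a dedicated item. The later reviews are mainly chart reviews, and the 8.1.7 step relies on the subject or personal physician to suspect a link.
- **Section 6.4 adds and does not restrict.** An admission elsewhere before Visit 3 is still an AE or SAE and can be elicited at Visit 3 or by telephone. The gain from widening 6.4 is earlier and more reliable capture.
- **The efficacy comparison is protected.** Ulcers are compared between arms through the primary endpoint, read blind on de-identified images (7 and 8.6). No formal between-arm AE test is planned. AE coding cannot bias the primary result.
- **A perforation forecast is tempting.** Multiplying 1:10 by an expected ulcer count would rest on 5 outside events and an unchanged lesion mix, although 1.2 says injury rates vary with center, EGD timing and technique.

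**Conclusion.** The point holds as a gap in safety ascertainment. Section 8.1.2 gives two answers for an asymptomatic ulcer, one of which can turn on an unblinded opinion. After Visit 3 (Day 16 to 60), recording of serious events depends on a relatedness judgement that can fall differently in the two arms.

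The effect cannot be sized as a number of missed events, because the documents' sources are 5.7 to 31 times apart. The direction under 8.1.2 cannot be predicted. Under 8.2 after Visit 3, the asymmetry would tend to record events in the device arm that go unrecorded in controls. This assumes that investigators attribute a control's late perforation to standard ablation, which the text permits but does not require. The change is worth making because it is cheap and the outcome is serious. The primary endpoint is unaffected.

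**What to change.** 1. **Section 8.1.2.** Reconcile the two sentences with one rule that depends on neither arm nor opinion, for example: *Any ulceration, perforation or fistula reported on the clinical or the research EGD read is recorded as an AE in both arms. Its course is documented from routine care and the planned study contacts, with no added endoscopy.* The trigger names the lesion and not the study grade, because under 3.1.2 the clinical report follows clinical guidelines and may not use Grades 1 to 4. The research images are read in batches (8.6), so some entries will be made late.
2. **Section 6.4.** Cover any emergency, inpatient or outpatient visit that the team learns of.
3. **Visit 3 and months 3, 6 and 12.** Add one yes/no item (esophageal perforation, fistula or related admission) to the visit, EMR reviews and calls already planned, recorded in both arms whatever the judged relatedness.

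**Cost.** Protocol wording, one CRF item and a few AE entries. If the registry's one-third ulcer share held and the device had no effect, 60 patients would give 60 × 0.18/3 = 3.6, 60 × 0.35/3 = 7.0 or 60 × 0.45/3 = 9.0 ulcers at the injury rates in 1.2 and 7.2. Some would be AEs already. The reported AE count would rise somewhat in both arms. The rule governs recording only, and clinical management of lesions stays with the treating team.
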